
 To evaluate the effect of mirikizumab CCI 
██████████ ██████████ clinical remission by CDAI or endoscopic remission in participants CCI
 
 CCI CCI 	
 Proportion of participants who achieve clinical remission by CDAI or endoscopic remission (analyzed separately) at AMAX Week 52 CCI 
██████████ ██████████
 
 Proportion of participants who achieve clinical remission by CDAI or endoscopic remission (analyzed separately) CCI 
██████████ ██████████

Objectives	Endpoints
CCI 
 • To assess the effect of mirikizumab in the achievement of endoscopic response CCI 	
 • Proportion of participants achieving endoscopic response in AMAX at: 
 ◦ Week 52 ◦ CCI

 • To assess the effect of mirikizumab in the achievement of endoscopic remission CCI 	
 • Proportion of participants achieving endoscopic remission in AMAX at: 
 ◦ Week 52 ◦ CCI

 • To assess the effect of mirikizumab on clinical response by PRO CCI 	
 • Proportion of participants achieving clinical response by PRO in AMAX at: 
 ◦ Week 52 ◦ CCI ◦ CCI

 • To assess the effect of mirikizumab on CCI 	
 • Proportion of participants achieving clinical remission by PRO in AMAX at: 
 ◦ Week 52 ◦ CCI ◦ CCI

 • To evaluate the effect of mirikizumab on CCI 	
 • Proportion of participants achieving clinical response by CDAI in AMAX at: 
 ◦ CCI ◦ Week 52 ◦ CCI ◦ CCI

 • To evaluate the effect of mirikizumab on CDAI remission CCI 	
 • Proportion of participants achieving clinical remission by CDAI in AMAX at: 
 ◦ CCI ◦ Week 52 ◦ CCI ◦ CCI

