
 To evaluate the effect of mirikizumab CCI CDAI remission CCI 	
 Proportion of participants achieving clinical remission by CDAI in AMAX at: 
 CCI Week 52 CCI CCI

 To assess the effect of mirikizumab CCI endoscopic response CCI 	
 Proportion of participants achieving endoscopic response in AMAX at: 
 Week 52 CCI

 To assess the effect of mirikizumab CCI endoscopic remission CCI 	
 Proportion of participants achieving endoscopic remission in AMAX at: 
 Week 52 CCI

 To assess the effect of mirikizumab CCI clinical response by PRO CCI 	
 Proportion of participants achieving clinical response by PRO in AMAX at: 
 Week 52 CCI CCI

 To assess the effect of mirikizumab CCI 	
 Proportion of participants achieving CCI in AMAX at: 
 Week 52 CCI CCI

 To evaluate the effect of mirikizumab CCI 
██████████ ██████████ clinical remission by CDAI or endoscopic remission in participants CCI :
 
 CCI CCI 	
 Proportion of participants who achieve clinical remission by CDAI or endoscopic remission (analyzed separately) at AMAX Week 52 CCI 
██████████ ██████████
 
 Proportion of participants who achieve clinical remission by CDAI or endoscopic remission (analyzed separately) CCI 
██████████ ██████████

Objectives	Endpoints
AMAM participants not achieving endpoints at Week 52 of AMAM:	

 To assess the effect of mirikizumab in the achievement of endoscopic response CCI 	
 Proportion of participants achieving endoscopic response in AMAX at: 
 Week 52 CCI

 To assess the effect of mirikizumab in the achievement of endoscopic remission CCI 	
 Proportion of participants achieving endoscopic remission in AMAX at: 
 Week 52 CCI

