5.4.1.2 Main Analytical Approach

Section 1.1 describes the proposed estimands to assess secondary objectives of this study.

The main analytical approach for binary secondary endpoints may be done similarly as for the primary endpoints and is described in Section 5.3.2. The main analytical approach for continuous secondary endpoints from Study AMAM participants will utilize ANCOVA as described in Section 5.1.1. Details are described in Appendix 2 in Section 6.2.

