6.2 Appendix 2: Description of Analyses

For each measure, analyses will be presented separately for each originating study and, for AMAM-originating participants will be summarized by intervention group in Study AMAX and intervention received in AMAM (see Section 5.1.4).

		Analysis Method	Population	
Measure	Variable	(Section 5.1.1)	(Section 4)	Time Point(s)
SES-CD	Endoscopic response	Descriptive analysis with NRI, mNRI and as Observed	PAS (primary) mITT (sensitivity) PAS – In participants with endoscopic response at W52 of originating study (sensitivity) PAS – In participants without endoscopic response at W52 of originating study	All visits with measurements in Complete Study Period
	Alternate Endoscopic remission SES- CD ≤ 4	Descriptive analysis with NRI, mNRI and as Observed Descriptive analysis with NRI, mNRI and as Observed	PAS - In participants with endoscopic remission at W52 of originating study PAS - In participants without endoscopic remission at W52 of originating study	All visits with measurements in Complete Study Period All visits with measurements in Complete Study Period
	SES-CD total score	Descriptive analysis with mBOCF and as Observed	PAS – In participants from Study AMAM	All visits with measurements in Complete Study Period

Measure	Variable	Analysis Method (Section 5.1.1)	Population (Section 4)	Time Point(s)
	Change from baseline in SES-CD total score	Descriptive analysis with ANCOVA and as Observed	PAS – In participants from Study AMAM	All visits with measurements in Complete Study Period
CDAI	Clinical remission by PRO	Descriptive analysis with NRI	PAS – In participants with clinical remission by PRO at W52 of originating study PAS – In participants without clinical remission by PRO at W52 of originating study	All visits with measurements in Complete Study Period
		Descriptive analysis with NRI and as Observed	PAS	All visits with measurements in Complete Study Period
	Clinical response by PRO	Descriptive analysis with NRI	PAS – In participants with clinical response by PRO at W52 of originating study PAS – In participants without clinical response by PRO at W52 in originating study	All visits with measurements in Complete Study Period
		Descriptive analysis with NRI as Observed	PAS	All visits with measurements in Complete Study Period

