	Clinical remission by CDAI	Descriptive analysis with NRI	PAS – In participants with clinical remission by CDAI at W52 of originating study PAS – In participants without clinical remission by CDAI at W52 of originating study	All visits with measurements in Complete Study Period
		Descriptive analysis with NRI, mNRI and as Observed	PAS	All visits with measurements in Complete Study Period

		Analysis Method	Population	
Measure	Variable	(Section 5.1.1)	(Section 4)	Time Point(s)
	Clinical response by CDAI	Descriptive analysis with NRI, mNRI and as Observed	PAS	All visits with measurements in Complete Study Period
	CDAI total score	Descriptive analysis with mBOCF and as Observed	PAS	All visits with measurements in Complete Study Period
	Change from baseline in CDAI total score	Descriptive analysis with ANCOVA and as Observed	PAS	All visits with measurements in Complete Study Period
	AP average	Descriptive analysis with mBOCF and as Observed	PAS	All visits with measurements in Complete Study Period
	Change from baseline in AP average	Descriptive analysis with ANCOVA and as Observed	PAS	All visits with measurements in Complete Study Period
	SF average	Descriptive analysis with mBOCF and as Observed	PAS	All visits with measurements in Complete Study Period
	Change from baseline in SF average	Descriptive analysis with ANCOVA and as Observed	PAS	All visits with measurements in Complete Study Period
Composite SES-CD and CDAI endpoints	Clinical remission by CDAI and endoscopic response	Descriptive analysis with NRI, mNRI, and as Observed	PAS – In participants with Clinical Remission by CDAI and Endoscopic Response at Week 52 of the Originating study	All visits with measurements in Complete Study Period

		Analysis Method	Population	
Measure	Variable	(Section 5.1.1)	(Section 4)	Time Point(s)
Measure Corticosteroid Free	Corticosteroid free Clinical Remission by CDAI	(Section 5.1.1) Descriptive analysis with NRI, mNRI, and as Observed	PAS – In participants taking corticosteroids at baseline and with CS free clinical remission by CDAI at W52 of originating study PAS – In participants taking	All visits with measurements in Complete Study Period
			corticosteroids at baseline and who did not achieve CS free clinical remission at CDAI at W52 of originating study	

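### SAP Appendix 2 names no non-achiever population for CDAI clinical response, although the endpoint sits under the objectives for AMAM participants who had not achieved endpoints at Week 52

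*Protocol*

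**What the plan says.** Protocol Section 3 opens a block of secondary objectives headed "AMAM participants not achieving endpoints at Week 52 of AMAM" and lists in it "Proportion of participants achieving clinical response by CDAI in AMAX at" Week 52 and redacted visits. SAP Section 1.1 repeats the heading and the endpoint. In the protocol synopsis the endpoint appears but the heading is redacted. In all three places the wording of the objective itself is partly redacted.

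For secondary endpoints, SAP Section 5.4.1.2 refers the reader onward: "Details are described in Appendix 2 in Section 6.2". The Appendix 2 row reads, in full, "Clinical response by CDAI Descriptive analysis with NRI, mNRI and as Observed PAS All visits with measurements in Complete Study Period". There is no second population line.

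The neighbouring CDAI remission variable has the line "PAS – In participants without clinical remission by CDAI at W52 of originating study", and the PRO response variable has "PAS – In participants without clinical response by PRO at W52 in originating study". SAP Appendix 3, which is the place to declare departures from the protocol's analyses, declares none.

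**The concern.** The objective concerns people who entered AMAX without the endpoint, and asks whether they gain it on AMAX mirikizumab. The population in Appendix 2 also contains people who may already have had it.

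This matters because SAP Section 5.1.2 measures efficacy from the originating-study baseline. SAP Appendix 1 defines CDAI response as a fall of at least 100 points from that baseline and/or a total of 150 or less. A participant who responded in AMAM and simply stayed in response therefore counts as an AMAX responder. A rate that blends maintained and new response cannot be read as the rate at which non-achievers respond.

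The trial is open-label, SAP Section 5.8.2 describes an interim analysis on unblinded data, and SAP Section 5.8.3 allows ad-hoc interims. A subset first chosen after such data have been seen would be post hoc.

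**Working it through.** The plan states no figure on this point, so the check is a comparison of text followed by an illustration of size.

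**Step 1: populations in SAP Appendix 2 for the endpoints in the non-achiever block.**

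| Endpoint | Population without the endpoint at originating-study Week 52? |
|---|---|
| Endoscopic response | Yes |
| Endoscopic remission (row labelled as the alternate definition) | Yes |
| Clinical remission by PRO | Yes |
| Clinical response by PRO | Yes |
| Clinical remission by CDAI | Yes |
| Change in CRP and in fecal calprotectin | Subset without endoscopic response |
| Clinical response by CDAI | No: PAS only |

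For PRO remission, PRO response and CDAI remission, a whole-PAS row is listed as well as the subset rows. Within this table, then, a bare PAS entry and a PAS subset entry mean different things.

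**Step 2: is the PAS already confined to non-achievers?** Its definition is redacted. But Appendix 2 divides it into participants with and without each sibling endpoint, so it is not restricted to non-achievers of those endpoints.

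**Step 3: do the display groups separate CDAI non-responders?** SAP Section 2 assigns AMAM participants to SC or IV-then-SC by endoscopic response at AMAM Week 52. SAP Section 5.1.4 displays results by AMAM treatment sequence and SC/IV group. An IV group can contain CDAI responders, and an SC group can contain CDAI non-responders.

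**Step 4: size of the difference within any one displayed group.** Let q be the share in CDAI response at AMAM Week 52, m the share of these in response in AMAX, and g the response rate among the rest.

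- Rate as the row is written: q·m + (1 − q)·g
- Rate for same-endpoint non-achievers: g
- Difference: q·(m − g), positive whenever m > g

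All three values are assumptions:

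- Small case, q 0.20, m 0.75, g 0.50: rate 0.150 + 0.400 = 0.550 against 0.500. Difference 0.20 × 0.25 = 0.05, or 5 points.
- Larger case, q 0.65, m 0.82, g 0.35: rate 0.533 + 0.1225 = 0.6555 against 0.35. Difference 0.65 × 0.47 = 0.3055, or about 31 points.

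**Step 5: what the documents offer on q.** Protocol Section 2.2.5 gives AMAM Week 52 CDAI remission, combined with Week 12 PRO response, as 263/579 = 45.4% on mirikizumab and 39/199 = 19.6% on placebo. These are composite remission rates among AMAM participants, not CDAI response rates among AMAX enrollees. They show that q may differ widely between treatment-sequence groups, but they do not fix it.

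**The case against.** The strongest reply is that the target population is not fully visible. The heading says only that endpoints were not achieved, and the objective's own text is redacted. The biomarker change endpoints in the same block are analysed, for AMAM, in participants without endoscopic response. If the CDAI response objective means that group too, the IV columns would largely supply it. This stands as a caveat: non-response on the same endpoint is a strong inference from the five sibling rows, not a certainty. Even so, the row should name its group, as the biomarker rows do.

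A second reply is that the SAP leaves room for the right analysis. Section 1.1 gives the estimand population as the PAS together with a specified sub-population, and Section 4 defines sub-populations generically. Appendix 2 is not exhaustive: it has no row for the separately defined endoscopic remission that is not labelled alternate. The table and figure specifications are in a separate document. A reader might infer from the bare PAS entry that a non-achiever analysis has been ruled out. The documents do not support that. They permit a subset, but they do not specify one for this endpoint.

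A third reply concerns size. A reader might picture one inflated pooled headline rate, but SAP Section 5.1.4 shows results by treatment sequence and SC/IV group, and pooled columns may be dropped. A reader might also take the 45.4% as a floor for q and conclude that the excess must be large. It is not a floor: the corresponding placebo figure is 19.6%, placebo and ustekinumab sequences are among the displayed groups, and the step from remission to response depends on a redacted remission cut-off.

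**Conclusion.** The point holds as a missing population specification. The protocol and SAP Section 1.1 place CDAI clinical response among the objectives for non-achievers. The operative analysis table gives it the whole PAS, no other passage names a subset for it, and no change from the protocol is declared. The mixing occurs inside each displayed group, because those groups are formed by treatment and endoscopic status and not by CDAI response.

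The direction rests on one assumption, that maintained response is more common than new response (m > g). The size cannot be established from the documents. The 5-point and 31-point cases show how far it can move under assumed values, and neither is an estimate. The conclusion also assumes that the redacted objective refers to non-achievers of CDAI response.

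The consequence is limited. This is one secondary endpoint in a study without hypothesis testing, and the co-primary endpoints are unaffected. It should still be corrected, because the rate as specified does not answer its objective.

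**What to change.** In SAP Appendix 2, add to "Clinical response by CDAI" a row restricted to PAS participants who were not in clinical response by CDAI at Week 52 of the originating study, modelled on the remission row that uses "without clinical remission by CDAI at W52 of originating study". State that this row is the analysis for the secondary objective. If the unredacted objective names a different non-achiever group, use that group instead.

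Add the matching row for participants who were in CDAI response at that visit, for parity with the sibling endpoints, and keep the whole-PAS row as descriptive. If the whole PAS was intended as the analysis for this objective, declare and justify that in SAP Appendix 3.

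The cost is two table rows and one further run of an existing program, with no new data collection. Where m exceeds g, the rate reported for this objective will be lower than the whole-PAS rate.

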1.3. Schedule of Activities (SoA)

1.3.1. Visit 1 through Visit 9 CCI

Table AMAX.1-1. Schedule of Activities - Visit 1 through Visit 9 CCI

Procedures	Schedule of Activities ^a										
Visit Number	V1 ^b		V2	V3	V4		V5	V6	V7	V8	V9
Visit Type	Office – Screening/ V1 ^a	Office - Dosing/V1 ^b	Office	Office	Phone	Office	Office	Office	Office	Office	Office
Week Relative to Study Drug Start ^c	CCI										
Day with Visit Tolerance Interval (VTI)											
All Participants (X); AMAM Rollover Participants Only (M); AMAG Rollover Participants Only (G); Optional (Opt) (See footnotes for additional key details)											
Informed consent	X										
Preexisting conditions	X	X									
Inclusion/Exclusion Criteria	X										
Concomitant medications	X ^{ae}	X	X	X		X	X	X	X	X	
Tobacco/Nicotine use	X ^f					X				X	
Demographics	X ^f										
AEs ^g (See Section 8.3)	X ^{ae}	X	X	X		X	X	X	X	X	
Phone Reminder ^e					X					X	
Physical Evaluation											
Vital signs (T, PR, BP) (See Section 8.2.1.)	X ^{ac, ag}	X ^{ag}	X	X		X	X	X	X	X	
Weight	X ^{af}					X				X	
Physical examination ^h (See Section 8.2.2.)	X ^{ae}	X	X	X		X	X	X	X	X	
CCI [REDACTED]	X ^f	X ^{ah}	X	X		X	X	X	X	X	
CCI [REDACTED]	X ^f	X ^{ah}	X	X		X	X	X	X	X	
Clinician CDAI (See Section 8.1.2.1.)	X ^{af}	X ^{ah}				X				X	
TB Risk Assessment Monitoring ⁱ	X ^{af}	X ^{ah}	X			X	X	X	X	X	

Procedures		Schedule of Activities ^a											
Visit Number	V1 ^b	V2		V3	V4		V5	V6		V7	V8	V9	
Visit Type	Office – Screening/ V1 ^a	Office - Dosing/V1 ^b	Office	Office	Phone	Office	Office	Office	Office	Office	Office	Phone	Office
Week Relative to Study Drug Start ^c	CCI												
Day with Visit Tolerance Interval (VTI)													
Laboratory Tests													
Chemistry	X ^{af}	X ^{ah}	X	X		X	X	X	X	X	X		X
Hematology	X ^{af}	X ^{ah}	X	X		X	X	X	X	X	X		X
Urine Pregnancy (local) ^j (See Section 8.2.7.1.)	X	X	X	X		X	X	X	X	X	X		X
Urinalysis	X ^k												
HIV testing	X												
HBV screening ^l (Section 8.2.8.)	X												
HBV DNA monitoring ^m	X ^{af}	X ^{ah}	X			X	X	X	X	X			X
HCV testing (See Section 8.2.9.)	X												
PK sample ⁿ	X ^{af}	X ^{ah}				X				X			X
Immunogenicity (ADA) samples ⁿ	X ^{af}	X ^{ah}				X			X				X
CCI	X ^f	X ^{ah}				X			X				X
Stool Samples (Note: Additional local stool testing [for example, ova and parasites] is allowed at the investigator's discretion.)													
Fecal calprotectin ^o	X ^f	X ^{ah}				X			X				X
Dispense stool collection kit ^o										M			
Take Home Patient Diary (Electronic)^p													
Patient electronic diary dispensed ^q	M												
Patient electronic diary returned ^r							M						
Take Home Patient Diary (Paper)^p													
Patient 14-Day paper diary dispensed ^{s,t}				G						X			
Patient 14-Day paper diary returned					G								X
On-Site Questionnaires (Paper)													
Patient 1-Day paper diary (24-hour recall) ^t	G		G	G			X	X	X	X			
CCI (See Section 8.1.2.2.)	M ^u	M ^{ah}				M							

Procedures	Schedule of Activities ^a										
	V1 ^b		V2	V3	V4		V5	V6	V7	V8	V9
Visit Number	Office – Screening/ V1 ^a	Office - Dosing/V1 ^b	Office	Office	Phone	Office	Office	Office	Office	Office	Phone
Visit Type											
Week Relative to Study Drug Start ^c	CCI										
Day with Visit Tolerance Interval (VTI)											
CCI (See Section 8.1.2.2.)	M ^u	M ^{ah}	M	M		M					
CCI (See Section 8.1.2.2.)	M ^u	M ^{ah}				M					
IBDQ	X ^v	X ^{ah}				X					X
CCI	X ^v	X ^{ah}				X					X
CCI	X ^v	X ^{ah}				X	X				X
CCI (See Section 8.2.11.)	X										

CCI CCI CCI

Abbreviations: ADA = antidrug antibody; AE = adverse event; AESI = adverse event of special interest; CCI [REDACTED]
AP = abdominal pain; CCI [REDACTED]; BP = blood pressure; CDAI = Crohn's Disease Activity Index; CDAI-AP = Crohn's Disease Activity
Index – Abdominal Pain; CDAI-SF = Crohn's Disease Activity Index – Stool Frequency; CCI [REDACTED] CT = computed
tomography; CXR = chest x-ray; CCI [REDACTED]
[REDACTED] HBcAb = hepatitis B core antibody; HBV = hepatitis B virus; HCV = hepatitis
C virus; HIV = human immunodeficiency virus; CCI [REDACTED] IBDQ = Inflammatory Bowel Disease Questionnaire;
IGRA = interferon gamma release assay; IP = investigative product; IV = intravenous; NA = Not applicable; NRS = numeric rating scale; CCI [REDACTED]
[REDACTED]; PI = principle investigator; PK = pharmacokinetic; PR = pulse rate; CCI [REDACTED]
SC = subcutaneous; CCI [REDACTED]
SoA = Schedule of Activities; T = temperature; TB = tuberculosis; TST = tuberculin skin test; V = Visit; VTI = visit tolerance interval;
CCI [REDACTED].

- a Please see detailed instructions provided by the sponsor for calculation of visit dates. Also, note that unscheduled assessments can be performed during scheduled visits, see [Table AMAX.1-3](#) for details.
- b V1 is a split visit, occurring on at least 2 office visits on different dates. Screening procedures are to be performed at the first part of V1, called Screening/V1a, in order to have results available to confirm eligibility prior to dosing. For AMAM-originating participants, it is recommended that V1a screening procedures be on the same date as AMAM V17. V1 dosing is performed at the Dosing/V1b visit. For both AMAM and AMAG-originating participants, the timing for AMAX V1a and V1b must allow for first AMAX dosing (V1b) within no more than CCI [REDACTED] from the last dosing in the originating study. It is required that all screening assessments, including laboratory test results are reviewed to confirm eligibility from both the final visit of the originating study as well as AMAX V1a, as applicable, prior to dosing at V1b. For participants originating from AMAM, the CCI [REDACTED]
[REDACTED] Note that some assessments may be required at both V1a and V1b. Refer to footnotes for details. To accommodate potential lab delays and/or needs for retesting, please plan for at least 10 business days to obtain lab results after initial samples are received at the laboratory, and up to 5 business days for endoscopy results after receipt of video.
- c All activities should be completed prior to any study drug administration unless otherwise stated.
- d See footnote b for definitions of the V1 Screening visit (V1a) and the V1 Dosing visit (V1b). V1 dosing (V1b) is defined as Day 1. All V1 screening activities need to be performed prior to dosing, including all assessment retesting (if needed), with results available prior to dosing such that the total interval from last dose in the originating study to first dose in AMAX is no more than CCI [REDACTED]. Please see detailed instructions provided by the sponsor for calculation of subsequent visit dates.
- e Site to remind participant to complete 14-Day diary and/or bowel prep, as appropriate. Phone reminder must occur at least 15 days prior to actual next visit date to ensure the participant begins the collection of diary data in time.
- f Data should be collected at V1 from the AMAG originating participants. Demographic data from the originator study can be used for AMAM participants. For all other items with AMAM participants: if data were collected at the final visit in AMAM, those data can be used in AMAX; otherwise, data should be collected at V1a.
- g For AESIs, additional data are collected (Section [8.3.7](#)).

- h Includes a symptom-directed evaluation as well as examination of eyes, heart, lungs, abdomen, and visual examination of the skin (Section 8.2.2).
- i At V1 and throughout the study, participants will be assessed for risk factors for TB (Section 10.5, Appendix 5). If the participant has a risk factor(s) or any TB-related signs or symptoms identified as part of the discussions of preexisting conditions or AEs, or as part of the standard physical exam, the investigator should conduct a thorough exam to evaluate for TB, including examination of peripheral lymph nodes and documentation of body temperature. If there are relevant physical findings or other factors that the investigator feels requires testing and imaging, an IGRA or TST and a CXR should be performed (Table AMAX.1-3 Unscheduled assessments). A CT scan can be performed as an alternative to the CXR, based on regional standard of practice (Section 8.2.6).
- j To be performed only on women of child-bearing potential. Done locally and at screening, as well as prior to each dosing (Section 8.2.7.1).
- k Data should be collected from the AMAM originating participants. If data were collected at the final visit in AMAG for AMAG-originating participants, they can be used, and there is no need to recollect at V1 in AMAX.
- l Participants testing HBcAb+ in the originator study do not need to have HBV full screening at V1 but they will need to have HBV DNA testing at screening and continue HBV DNA monitoring throughout the trial. All other participants should have the full HBV screening at V1a.
- m Perform only if participant had ongoing monitoring for HBV DNA during their originator study, or for participants who were found to be HBcAb+ in AMAX and met the requirements to continue in the study as described in Section 8.2.8. Such participants will undergo monitoring of HBV DNA at specified intervals. Any participants not meeting the requirements to continue in the study at any time must be discontinued from the study and receive appropriate follow-up medical care (Section 8.2.8).
- n Samples will be collected predose on the days specified in the SoA. Additionally, in the event of a systemic allergic/hypersensitivity event, blood samples will be collected for PK, ADA, CCI [REDACTED] at the following time points: as close as possible to: (1) the onset of the systemic allergic/hypersensitivity event, CCI [REDACTED] [REDACTED]
[REDACTED]
- o Participants must adhere to proper stool incubation requirements and return stool to site within 24 hours of producing sample. AMAG and AMAM participants dispensed pre-endoscopy stool collection kit per SoA. AMAG participants should also receive stool collection kit at the visit prior to the endoscopy performed at CCI [REDACTED]. Instruct participants to collect stool samples up to 3 days prior to beginning bowel prep for endoscopy. For stool collection for testing associated with other visits, the sample collection kits may be sent home in earlier visits. This allows the participants to collect samples within 24 hours prior to their visit and bring to the site on the day of visit. If samples are not collected before or on the day of the visit, the collection kit should be sent home with the participant on the day of the visit, and sample should be collected as soon as possible and returned to the site within 24 hours of producing the sample. For AMAG-originating participants at V1, the collection may be performed at the first day of screening and must be collected prior to dosing.
- p Visits will differ for participant collections via paper diary or electronic diary capture. See Section 8.1.2.2 for instructions.
- q Dispensed at V1a to AMAM participants only. Includes CCI [REDACTED] CDAI-SF with Bristol Stool Scale, CDAI-AP, CDAI well-being, CCI [REDACTED] [REDACTED] (See Section 8.1.2.2).

- r Collected only from AMAM participants.
- s The CCI [REDACTED] endoscopy should be performed for AMAG-originating participants CCI [REDACTED] (See [Table AMAX.1-3](#)) and is notated here under V1 only as a reminder, since it could occur over a wide window of time within the AMAX schedule. At the visit prior to the CCI [REDACTED] endoscopy, the site should provide the participant with one 14-Day paper diary to be returned at the next regularly scheduled office visit. The 14-Day diary should be completed in the 14 days leading up to the next regularly scheduled office visit and may begin before or after the endoscopy, depending on endoscopy timing (See [Table AMAX.1-3](#))
- t The 14-Day paper diaries and 1-Day paper diaries both include: CCI [REDACTED] CDAI-SF with Bristol Stool Scale, CDAI-AP, CDAI well-being, CCI [REDACTED] (See Section [8.1.2.2](#)).
- u Collections required only for participants from AMAM. Collect at AMAX V1a if data were not collected at the final visit in the originator study.
- v Collect at AMAX V1a if data were not collected at the final visit in the originator study.
- w At V1a of AMAX, participants from AMAM should be administered the CCI [REDACTED]. Participants from AMAG should be administered the CCI [REDACTED]
- x CCI [REDACTED]
- y [REDACTED]
- z Visit procedures and assessments must be completed prior to dosing. For both AMAM and AMAG-originating participants, dosing at V1b should occur no later than CCI [REDACTED] after the participant's last dose in the originator study.
- aa Dispense study drug at each office visit for the next CCI [REDACTED] dose(s) as needed, noting that the visit schedule changes from every CCI [REDACTED] Also, see [Table AMAX.1-4](#) and Section [6.1](#) regarding timing for administrations between scheduled office visits and participants who choose not to self-administer. At Visit 4, provide ancillary supplies. Continue to dispense ancillary supplies at each visit as needed. Note that any used or unused study drug may be returned as an optional unscheduled activity at subsequent visits ([Table AMAX.1-3](#)).
- ab Site to complete training with the participant using the *Patient Study Drug Administration Training Log* at Visit 4. If training does not occur at Visit 4, the participant should be trained at the earliest opportunity based on the PI's discretion. Additionally, participants may be retrained on how to self-administer the investigational product, if needed.
- ac Site to complete and dispense *Patient Study Drug Administration Log*. Provide syringes for next dosing, inform participant of dosing date for self-injection, and provide ancillary supplies to participant.

- ad Participant to return the *Patient Study Drug Administration Log* at the next visit.
- ae Assessments are scheduled to be performed at the last visit of the originating study and will only need to be performed separately for AMAX V1a if these visits do not occur on the same date.
- af Collect/assess at AMAX V1a if not performed at the last visit of the originator study.
- ag Vitals should be assessed at both V1a and V1b. However, only vitals data from V1b should be entered into Inform for V1.
- ah If more than **CCI** will have elapsed between last collection/assessment and the first AMAX dosing, additional procedures must be performed again prior to the V1b dosing. See sponsor guidance regarding sample collection kits or data entry for items that need to be collected again at V1b. Investigator medical judgment should be used regarding whether the repeat lab results should be available and reviewed prior to dosing (review prior to dosing not needed for PK, immunogenicity, **CCI** or fecal calprotectin).

1.3.2. Visit 10 through Visit 19 **CCI**Table AMAX.1-2. Schedule of Activities - Visit 10 through Visit 19 **CCI**

Procedures	Schedule of Activities ^a													
	V10	V11	V12		V13	V14		V15	V16		V17	V18	V19 ^r	
Visit Number	Office	Office	Phone	Office	Office	Phone	Office	Office	Phone	Office	Office	Office	Phone	Office
Visit Type	Office	Office	Phone	Office	Office	Phone	Office	Office	Phone	Office	Office	Office	Phone	Office
Week Relative to Study Drug Start ^b	CCI													
Day with Visit Tolerance Interval (VTI)	CCI													
All Participants (X); AMAM Rollover Participants Only (M); AMAG Rollover Participants Only (G); Optional (Opt) (See footnotes for additional key details)														
Concomitant medications	X	X		X	X		X	X		X	X	X		X
Tobacco/Nicotine use							X							X
AEs ^d (See Section 8.3)	X	X		X	X		X	X		X	X	X		X
Phone Reminder ^c			X			X			X				X	
Physical Evaluation														
Vital signs (T, PR, BP) (See Section 8.2.1.)	X	X		X	X		X	X		X	X	X		X
Weight				X			X			X				X
Physical examination ^e (See Section 8.2.2.)	X	X		X	X		X	X		X	X	X		X
CCI .)	X	X		X	X		X	X		X	X	X		X
CCI .)	X	X		X	X		X	X		X	X	X		X
Clinician CDAI (See Section 8.1.2.1.)				X			X			X				X
TB Risk Assessment Monitoring ^f	X	X		X	X		X	X		X	X	X		X

Procedures	Schedule of Activities ^a													
	V10	V11	V12		V13	V14		V15	V16		V17	V18	V19 ^c	
Visit Number	Office	Office	Phone	Office	Office	Phone	Office	Office	Phone	Office	Office	Office	Phone	Office
Visit Type														
Week Relative to Study Drug Start ^b														
Day with Visit Tolerance Interval (VTI)														
Laboratory Tests														
Chemistry	X	X		X	X		X	X		X	X	X	X	
Hematology	X	X		X	X		X	X		X	X	X	X	
Urine pregnancy (local) ^g (See Section 8.2.7.1.)	X	X		X	X		X	X		X	X	X	X	
HBV DNA monitoring ^h	X	X		X	X		X	X		X	X	X	X	
PK sample ⁱ				X			X			X			X	
Immunogenicity (ADA) samples ^j				X			X			X			X	
CCI				X			X			X		X	X	
Stool Samples (Note: Additional local stool testing [for example, ova and parasites] is allowed at the investigator's discretion.)														
CCI				X			X			X		X	X	
Dispense stool collection kit ^k												X		
Take Home Patient Diary (Paper)														
Patient 14-Day paper diary dispensed ^{k,l}		X			X			X			X			
Patient 14-Day paper diary returned				X			X			X			X	
On-Site Questionnaires (Paper)														
Patient 1-Day paper diary (24-hour recall) ^l	X	X			X			X			X	X	X	
CCI							X						X	
							X						X	

Abbreviations: ADA = antidrug antibody; AE = adverse event; AESI = adverse event of special interest; A₁ CCI₁
[REDACTED]; BP = blood pressure; CDAI = Crohn's Disease Activity Index; CDAI-AP = Crohn's Disease Activity Index – Abdominal
Pain; CDAI-SF = Crohn's Disease Activity Index – Stool Frequency; CT = computed tomography; CXR = chest x-ray; CCI₂
ETV = early termination visit; CCI₃ [REDACTED]; HBcAb = hepatitis B core antibody;
HBV = hepatitis B virus; CCI₄ [REDACTED]; IBDQ = Inflammatory Bowel Disease Questionnaire; IGRA = interferon gamma
release assay; IP = investigational product; CCI₅ [REDACTED]; PK = pharmacokinetic; PR = pulse rate; CCI₆

SoA = Schedule of Activities; T = temperature; TB = tuberculosis; TST = tuberculin skin test; V = visit.

- a Please see detailed instructions provided by the sponsor for calculation of visit dates. Also, note that unscheduled assessments can be performed during scheduled visits, see [Table AMAX.1-3](#) for details. Please refer to Section [10.13.3](#) for continued access period details.
- b All activities should be completed prior to any study drug administration unless otherwise stated.
- c Site to remind participant to complete 14-Day diary and/or bowel prep, as appropriate. Phone reminder must occur at least 15 days prior to actual next visit date to ensure the participant begins the collection of diary data in time.

- d For AESIs, additional data are collected (See Section 8.3.7).
- e Includes a symptom-directed evaluation as well as examination of eyes, heart, lungs, abdomen, and visual examination of the skin (Section 8.2.2).
- f Throughout the study, participants will be assessed for risk factors for TB (Section 10.5, Appendix 5). If the participant has a risk factor(s) or any TB-related signs or symptoms identified as part of the discussions of AEs or as part of the standard physical exam, the investigator should conduct a thorough exam to evaluate for TB, including examination of peripheral lymph nodes and documentation of body temperature. If there are relevant physical findings or other factors that the investigator feels warrant testing and imaging, an IGRA or TST and CXR should be performed (Table AMAX.1-3 Unscheduled assessments). A CT scan can be performed as an alternative to the CXR based on regional standard of practice (Section 8.2.6).
- g To be performed only on women of child-bearing potential. Done locally and prior to dosing (Section 8.2.7.1). Between visits, urine pregnancy tests are to be performed prior to monthly at-home dosing.
- h Perform only if participant had ongoing monitoring for HBV DNA during their originator study, or for participants who were found to be HBcAb+ in AMAX and met the requirements to continue in the study as described in Section 8.2.8. Such participants will undergo monitoring of HBV DNA at specified intervals. Any participant not meeting the requirements to continue in the study at any time must be discontinued from the study and receive appropriate follow-up medical care (Section 8.2.8).
- i Samples will be collected predose on the days specified in the SoA. Additionally, in the event of a systemic allergic/hypersensitivity event, blood samples will be collected for PK, ADA, CCI [REDACTED] at the following time points: as close as possible to: (1) the onset of the systemic allergic/hypersensitivity event, (2) the resolution of the systemic allergic/hypersensitivity event, CCI [REDACTED]
[REDACTED]
- j Participants must adhere to proper stool incubation requirements and return stool to site within 24 hours of producing sample. AMAG-originating participants should receive stool collection kits in AMAX at the visit CCI [REDACTED], AMAG- and AMAM-originating participants are dispensed a stool collection kit per SoA. Instruct participants to collect stool samples up to 3 days prior to beginning bowel prep for endoscopy. For stool collection for testing associated with other visits, the sample collection kits may be sent home in earlier visits. This allows the participants to collect samples within 24 hours prior to their visit and bring to the site on the day of visit. If samples are not collected before or on the day of the visit, the collection kit should be sent home with the participant on the day of this visit, and sample should be collected as soon as possible and returned to the site within 24 hours of producing the sample.
- k At the visit CCI [REDACTED], the site should provide the participant with one 14-Day paper diary to be collected at the next regularly scheduled office visit. The 14-Day diary should be completed in the 14 days leading up to the next regularly scheduled office visit and may begin before or after the endoscopy, depending on endoscopy timing (see Table AMAX.1-3).
- l The 14-Day paper diaries and 1-Day paper diaries both include: CCI CDAI-SF with Bristol Stool Scale, CDAI-AP, CDAI well-being, CCI [REDACTED]
[REDACTED] (See Section 8.1.2.2.)

m **CCI**

- n Visit procedures and assessments must be completed prior to dosing.
- o Dispense study drug at each office visit for the next **CCI** [REDACTED] as needed, noting that the visit schedule changes from every **CCI** [REDACTED]. Also, see [Table AMAX.1-4](#) and Section 6.1 regarding timing for administrations between scheduled office visits and participants who choose not to self-administer. Continue to dispense ancillary supplies at each visit as needed. Note that any used or unused study drug may be returned as an optional unscheduled activity at subsequent visits (see [Table AMAX.1-3](#)).
- p Site to complete and dispense *Patient Study Drug Administration Log*. Provide syringes for next dosing, inform participant of dosing date for self-injection, and provide ancillary supplies to participant.
- q Participant to return the *Patient Study Drug Administration Log* at the next visit.
